### 10.2.1 Exceptions to AE Documentation in OnCore

Laboratory abnormalities (e.g., clinical chemistry, hematology, and urinalysis) without clinical significance are not recorded as AEs or SAEs with the exception of abnormalities that meet the definition of DLT per Section 6.3.

Other abnormal assessments (e.g., vital signs, ECG, X-rays) that are not associated with signs or are considered of no clinical significance do not need to be recorded unless they are a targeted toxicity.

Clinical significance is defined as requiring medical or surgical intervention or leading to a study treatment delay or discontinuation. Any laboratory or other assessments meeting the definition of clinically significant must be recorded as an AE, as well as an SAE, if applicable.

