# 1.2 Secondary Objectives

Secondary objectives of this protocol are:

- Determine safety and feasibility of repeat dosing of HCW9218 as outlined by incidence of adverse events (AEs) based on CTCAE v5.
- Estimate response rate (complete response (CR), partial response (PR) or stable disease (SD)) as a primary efficacy objective.
- Estimate progression free survival (PFS) and overall survival (OS) at 6 months and 1 year from 1st dose of HCW9218.

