# 12.2 Secondary Endpoints

The safety of repeat dosing of HCW9218 is adverse events (AEs) based on CTCAE v5.

Response and progression endpoints are based on the Response Evaluation Criteria in Solid Tumors (RECIST) 1.1.

- Response rate (CR, PR or SD) at 3 months, 6 months and 12 months
- Progression-free survival (PFS) by 6 month and 1 year is defined as the duration of time from start of treatment to time of progression or death, whichever occurs first
- Overall survival (OS) at 6 month and 1 year from 1st dose of HCW9218 is defined as patients alive at 1 year

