# 13.2 Statistical Analysis

The primary analysis study population will be intent-to-treat in that all patients receiving the 1st injection of HCW9218 will be evaluable for toxicity and efficacy.

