# **Secondary Endpoints**

If there are sufficient numbers, the secondary endpoints of overall survival and progression-free survival by 6 months and 1 year will be estimated with Kaplan-Meier curves. The primary efficacy endpoint of response rate will be estimated by a simple proportion with 95% confidence limits if sufficient numbers exist. Safety will be estimated by the proportion of adverse events based on CTCAE v5. Further descriptive statistics and plots such as boxplots, spaghetti plots and swimmer plots will be used to assess kinetics and other markers of efficacy such as immune based monitoring and toxicity.

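### Section 10.2.1 keeps observed-only laboratory abnormalities of any grade out of the AE record, and Section 13.2 specifies no graded laboratory summary to make up for it

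*Combined protocol and SAP*

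**What the plan says.** Section 1.2 sets the objective: "Determine safety and feasibility of repeat dosing of HCW9218 as outlined by incidence of adverse events (AEs) based on CTCAE v5". Section 12.2 gives the endpoint without unit, grade or period: "The safety of repeat dosing of HCW9218 is adverse events (AEs) based on CTCAE v5".

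The table in Section 10.2 calls for AEs of Grade 2 or higher, whatever the attribution, through the End of Treatment visit, subject to the exceptions in Section 10.2.1. There, laboratory abnormalities "without clinical significance are not recorded as AEs or SAEs with the exception of abnormalities that meet the definition of DLT". Clinical significance is defined as "requiring medical or surgical intervention or leading to a study treatment delay or discontinuation". The section also imposes a duty in the other direction: "Any laboratory or other assessments meeting the definition of clinically significant must be recorded as an AE".

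Section 6.3 confines DLTs to the 21 days after the first dose, closed by the Cycle 2 Day 1 assessment and laboratory results.

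Section 13.2 opens by making "all patients receiving the 1st injection of HCW9218 will be evaluable for toxicity and efficacy". Its safety estimator is one sentence: "Safety will be estimated by the proportion of adverse events based on CTCAE v5". Descriptive statistics and plots follow for kinetics, immune monitoring and toxicity, with no mention of laboratory values by CTCAE grade.

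**The concern.** The objective is graded by CTCAE, but the rule that decides which laboratory findings become AEs takes no account of grade. The one protection for severe findings that need no action, the DLT exception, expires before repeat dosing begins. The safety result most relevant to giving further cycles could then omit laboratory toxicity that was measured and seen.

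The omission is foreseeable. Appendix II lists lymphocyte, neutrophil, platelet and white-cell decreases and ALT and AST increases as reported with related agents. Section 7.1 says that combining the two activities in one molecule may bring more frequent or more severe AEs.

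A second, smaller weakness is that the estimator sentence in Section 13.2 names neither the unit counted nor the denominator, although the objective speaks of incidence.

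**Working it through.** **1. Is there a figure to reproduce?** No. The plan gives no expected AE incidence, precision or sample size for this estimate. The only check is on the possible denominator. The N columns of Table 2 (Section 13.3) sum to 0+1+1+1+9 = 12 and 3+6+9+5+1 = 24, matching the enrollment goal of 12 to 24.

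**2. Which laboratory abnormalities are entered as AEs?** Sections 10.2, 10.2.1 and 6.3 read together:

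| Laboratory abnormality | Entered as an AE? |
|---|---|
| Any cycle, intervention needed | Yes |
| Any cycle, dose delayed or treatment stopped | Yes |
| Cycle 1, meets the DLT definition | Yes |
| Cycle 1, Grade 3–4 but DLT-exempt, no action taken | No |
| Cycle 2 onward, any grade, no action taken | No |

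The fourth row includes Grade 4 lymphopenia or leukopenia, and isolated Grade 3 ALT or AST elevation, that recovers within 7 days as Section 6.3 requires. It also includes Grade 3 amylase or lipase without signs of pancreatitis.

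**3. Does anything else capture the last two rows?**
- *Dose delay.* In Section 6.1.1 the conditions that oblige a delay include no laboratory criterion. Delay for ongoing treatment-related toxicity is optional. Two patients with the same Grade 3 value can therefore be recorded differently.
- *Targeted Toxicity Worksheet.* Appendix IV has no laboratory items, and Section 10.2.2 ends its use at Cycle 1 Day 5.
- *Section 13.2 plots.* They are generic and do not specify CTCAE grades.
- *Raw values.* These are obtained. Section 8.1 schedules the blood count at every Cycle 1 and Cycle 2 visit, on Day 1 of later cycles and at End of Treatment. The metabolic panel is scheduled on Days 1 and 8 of Cycle 1, on Day 1 of each later cycle and at End of Treatment. The plan does not commit to summarising them by grade.

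**4. Direction and size.** Let p be the true per-patient incidence of a laboratory event and f the share of affected patients whose event never meets the recording test. Neither is in the documents, so the values below are assumptions.

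Recorded incidence = p(1 − f)

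| p | f = 25% | f = 50% | f = 75% |
|---|---|---|---|
| 50% | 37.5% | 25% | 12.5% |
| 25% | 18.75% | 12.5% | 6.25% |

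The factor (1 − f) never exceeds 1, so the error runs one way: none at f = 0, complete loss of the term at f = 1.

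The chance that n patients yield no recorded case is (1 − p(1 − f))^n. With p = 25% and f = 50%:
- n = 12: 0.875^12 = 20.1%, against 0.75^12 = 3.2% if every case were recorded.
- n = 24: 0.875^24 = 4.1%, against 0.75^24 = 0.1%.

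These treat all n patients as dosed in the period. Fewer will be if some stop after Cycle 1.

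**5. Unit of the estimator.** Assume 24 treated patients and 60 AEs in total, with one term affecting 6 patients twice each. Patients affected: 6/24 = 25.0% (exact 95% CI 9.8% to 46.7%). Share of AEs: 12/60 = 20.0%. Episodes per patient: 12/24 = 0.50. The sentence in Section 13.2 does not say which is meant.

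**The case against.** Leaving laboratory values without clinical consequence out of AE listings is a disclosed and defined rule. Anything leading to intervention, delay or discontinuation must be recorded. The safety summary is descriptive, in 12 to 24 patients. Blood counts with differential are frequent, lymphocyte number is a correlative objective in Section 1.3, and plots covering toxicity are planned. A severe cytopenia is therefore unlikely to pass unseen by the study team. With one patient at each of dose levels 1 to 3 in the expected scenario of Table 2, a table by dose level would be sparse. An added laboratory table would also leave Section 10.2.1 as it is.

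Much of this stands. The gap is in what the analysis plan commits to report, not in what clinicians see. But a rule that removes findings from the AE record regardless of grade needs a graded laboratory summary beside it, and none is specified. Sparse cells limit inference from the table, not its use as a record.

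A reader might infer more than the text supports:
- *That safety has no patient denominator, or is defined as a share of events.* Section 13.2 makes every patient given the first injection evaluable for toxicity, and the objective says incidence. The estimator sentence states no event denominator either. It is ambiguous, and the patient reading fits the section better.
- *That all laboratory toxicity without intervention is lost.* Delay, discontinuation or DLT status is enough for recording.
- *That Cycle 1 is complete.* It is not, because of the DLT-exempt events.
- *That no laboratory analysis is planned.* Generic descriptive summaries are; the graded table is what is missing.

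**Conclusion.** The point holds within limits. Followed exactly, the plan leaves out of AE incidence any laboratory abnormality, whatever its grade, that needs no intervention, causes no delay or discontinuation and is not a DLT. This bears most on Cycle 2 onward, where the DLT exception no longer applies, and also on DLT-exempt findings in Cycle 1. For laboratory terms the incidence can only be understated. The amount depends on p and f, which the documents do not give, so the figures above illustrate the mechanism and do not predict the result.

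The conclusion does not extend to the MTD, because DLT abnormalities are recorded, or to overall AE incidence: the laboratory sentence does not touch non-laboratory AEs of Grade 2 or higher. The estimator wording alone would merit only a clarification. The missing graded laboratory table is the substantive part, and it is worth adding because it is cheap and offsets a one-directional error.

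**What to change.** In Section 13.2:

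1. Add a table of worst post-baseline CTCAE grade against baseline grade for the blood count and metabolic panel values already scheduled. Present it by dose level and by period (Cycle 1 versus Cycle 2 onward), irrespective of whether an AE was entered, with patients dosed in the period as the denominator. Count the Cycle 2 Day 1 sample that closes the DLT period under Cycle 1. Amylase and lipase are routine only at baseline and Cycle 1 Day 8, so they can be added for Cycle 1 alone.
2. State the AE estimator as the number and percentage of treated patients with at least one event, by CTCAE term and maximum grade.

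Section 10.2.1 can stay as written. AE incidence will still omit these findings, but the laboratory table will show them alongside.

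No new tests or AE entries are needed. The cost is extraction and tabulation of laboratory values; Sections 11.1 and 11.2 do not say whether these are already in the case report forms. The resulting safety profile may look less favourable.

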# 10.2.2 Targeted Toxicity Worksheet

The targeted toxicity worksheet is done in addition to AE documentation as described in the table in Section 10.2. It is a focused assessment during the DLT period. The highest grade of toxicity since the last assessment is recorded (which for outpatients may be patient reported). The targeted toxicity worksheet is completed at each of the following timepoints based on an in person assessment at that timepoint:

- Cycle 1 Day 1
  - o Prior HCW9218 injection (within 1 hour prior)
  - At 3 hours (±15 minutes) post injection
  - At 6 hours (±15 minutes) post injection
- Cycle 1 Day 2
- Cycle 1 Day 3
- Cycle 1 Day 5

The completion of the targeted toxicity worksheet aligns with in person visits and may be shifted to align with the actual day a visit occurs or skipped if a visit is not occurred.

# 10.3 Required Reporting: IRB, HCW Biologics and FDA

Certain events or situations require rapid (expedited) reporting as summarized in the table below as well as reporting to the FDA as a part of the IND annual report.

Agency reporting to	Criteria for reporting	Timeframe	Form to Use	Submit to
U of MN IRB	Unanticipated death of a locally enrolled subject(s); New or increased risk; Any adverse event that requires a change to the protocol or consent form – refer to the IRB website for complete details	5 Business Days	RNI	ETHOS
	Deviations that occur at UMN as defined in Section 14.1	Per current IRB requirements	OnCore Deviation Form and IRB Report Form	
FDA	Unexpected and fatal or unexpected and life threatening suspected adverse reaction  1) Serious, unexpected, and suspected adverse reaction or 2) Increased occurrence of serious suspected adverse reactions over that listed in the investigator brochure or 3) Findings from other sources (other studies, animal or in vitro testing) – not applicable for this study	No later than 7 Calendar Days  No later than 15 Calendar Days	University of Minnesota SAE Report	Submit to FDA as an amendment to IND with a copy to HCW Safety Reporting <[contact]></[contact]>
	All other events per CFR 312.32	At time of annual report	FDA Annual report	Submit to FDA as an amendment to IND
HCW Biologics	Any event meeting the definition of an SAE	Within 24 hours of study team knowledge	University of Minnesota SAE Report	Submit to: HCW Safety Reporting <[contact]></[contact]>

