# **Study Synopsis**

# A Phase I Study of HCW9218, a Bifunctional TGF-β Antagonist/IL-15 Protein Complex, in Select Advanced Solid Tumors After Failing at Least Two Prior Therapies

Study Overview:	This is a single center, Phase I dose finding study of HCW9218 for the treatment of select advanced solid tumor cancers, including, but not limited to breast, ovarian, prostate and colorectal. Pancreatic cancer is excluded due to a competing HCW9218 protocol. Primary brain tumors are not eligible.  HCW9218 is a novel bi-functional fusion protein complex administered by subcutaneous (SC) injection. It is comprised of a soluble fusion of two human TGFβRII domains, human tissue factor, and human IL-15, and a second soluble fusion of two human TGFβRII domains and a sushi domain of human IL-15Rα. HCW9218 activates IL-15R signaling on effector immune cells and the dimeric TGFβRII functions as a "trap" for all three human TGF-β isoforms.  HCW9218 is administered by subcutaneous injection in the outpatient setting once every 3 weeks for a minimum of two cycles unless medically contraindicated or the participant wishes to discontinue. Treatment may continue until disease progression, unacceptable toxicity, patient refusal, or treatment is felt to be no longer of benefit. Patients are followed for 1 year from the 1st dose of HCW9218 to determine progression free survival (PFS) and overall survival (OS). The primary analysis will be intent-to-treat from the point of 1st injection of HCW9218 both for toxicity and efficacy.  Up to 5 dose levels of HCW9218 will be tested (including a safety (-1) level in the event of unexpected toxicity) to identify the maximum tolerated dose (MTD) with a small expansion cohort of the MTD or Dose Level 4 if no dose limiting toxicity is encountered.
Investigational Product (IP):	HCW9218 provided by HCW Biologics, Inc.
Study Rationale:	HCW9218 potently activates natural killer (NK) cells and CD8 + T cells in vitro and in vivo to promote their proliferative and metabolic activities and enhance their cytotoxicity against tumor targets. The fusion complex also exhibits TGF-β neutralizing activity in vitro and sequesters plasma TGF-β in vivo. It is hypothesized that HCW9218 may serve as a novel therapeutic to simultaneously provide immunostimulation and lessen immunosuppression associated with solid tumors.

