# 2.2.3 Summary of Clinical Findings

HCW9128 has not yet been evaluated in human clinical studies. The published adverse event (AE) profiles of related immunotherapeutics, including recombinant IL-2, recombinant human IL-15 (rhIL-15), IL-15 mutein/IL-15RαSu-Fc complex (ALT-803, nogapendekin alfa inbakicept), TGFβRII-Fc fusion (AVID200), TGFβRII-anti-PD-L1 IgG1 fusion (M7824, bintrafusp alfa) and anti-TGF- $\beta$  antibody (fresolimumab), are provided in Appendix II. These agents contain protein domains that are similar in structure and/or mechanism-of-action as those of HCW9218. See additional information in the IB.

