# 11.3 Data and Safety Monitoring Plan

The study's Data and Safety Monitoring Plan will be in compliance with the University of Minnesota Masonic Cancer Center's Data & Safety Monitoring Plan (DSMP), which can be accessed at https://z.umn.edu/dsmp.

For the purposes of data and safety monitoring, this study is classified as high risk (Phase I under a locally sponsored IND). Therefore the following requirements will be fulfilled:

- The Masonic Cancer Center Data and Safety Monitoring Council (DSMC) will review the study's progress quarterly with the understanding the Cancer Protocol Review Committee (CPRC).
- The Masonic Cancer Center PI will comply with at least twice yearly monitoring of the project by the Masonic Cancer Center monitoring services.

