## 11.4 Regular Team Meetings to Review Safety

Regular meetings will be held to facilitate communication regarding the study's progress in terms of individual patient safety including events meeting the definition of dose limiting toxicity, excessive toxicity (early study stopping rule for CRM only), serious adverse events (SAEs) and overall impact on future enrollment.

At a minimum each patient is reviewed at the end the 1st 21 days to document the DLT status and to confirm the timing and dose level for the next patient cohort enrolled.

The outcome of these discussion will be documented in the meeting minutes and the statistician or designee will send out a confirmatory email summarizing the discussion which will become part of the regulatory record.

Other issues for discussion may include pending patients, patient updates, summary of safety reports, and case report form completion.

The CRC or CRC-RN or designee is responsible for arranging these meetings and preparing the agenda. Meetings will occur every 2 weeks; however, these may be scheduled more or less frequently at the discretion of the PI and/or study staff. The

safety discussion may be part of the regular PI meeting but must be documented as above (in study minutes and post-meeting email from the statistician or designee).

Expected participation includes the Principal Investigator, the study statistician or designee and relevant CTO staff (CRC-RN, CRC, Regulatory Specialist, and Program Manager) or appropriate designee.

In the situation of a patient completing the DLT period between scheduled meetings, communication via email may be used in lieu of a meeting provided the patient was discussed at the prior meeting and will be included on the next meeting's agenda.

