- Cohort 4 is completed without a pre-defined AE or a DLT neither Step 2 nor Stage 2 is used if a total of 9 patients are enrolled in Cohort 4 to complete the study.

Stage 2 is initiated at the 1st DLT. The study design changes to an application of the continual reassessment method (CRM) with an informative skeleton based on constrained maximum likelihood estimation (lasonos & O'Quigley, 2012). Enrollment occurs in cohorts of three patients. Each new cohort of three patients are sequentially assigned to the most appropriate dose by the study statistician based on the updated toxicity probabilities once the 3rd patient in a cohort reaches Day 21 (DLT period). The goal will be to identify one of the 5 dose level strategies corresponding to the desired maximum toxicity rate of ≤25%. The MTD will be identified by the minimum of the following criteria: (1) the total Stage 2 sample size of 24 is exhausted or (2) 9 consecutive patients are enrolled at the same dose. The function 'crm' from the R package 'dfcrm' will calculate posterior means of toxicity probabilities. Dose escalation of more than one level is not permitted with this design.

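### Section 10.3 switches off 15-day FDA reporting of findings from other studies and nonclinical work, and Section 11.4 does not require such findings to be reviewed at cohort decisions

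*Combined protocol and SAP*

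**What the plan says.** The FDA part of the table in Section 10.3 gives three triggers for a report within 15 calendar days. The first is a serious, unexpected, suspected adverse reaction. The second is a rise in serious suspected reactions above what the brochure lists. The third reads "Findings from other sources (other studies, animal or in vitro testing) – not applicable for this study". No reason is given for the qualifier after the dash.

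The Synopsis, and Section 3 in the same words, state: "Pancreatic cancer is excluded due to a competing HCW9218 protocol". Section 11.3 says that "this study is classified as high risk (Phase I under a locally sponsored IND".

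For the supplier, Section 10.3 requires that "Any event meeting the definition of an SAE" go from the study team to HCW Biologics within 24 hours. It describes no flow in the other direction.

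For cohort decisions, Section 11.4 requires that each patient's DLT status be reviewed after the first 21 days and that the timing and dose level of the next cohort be confirmed. Safety reports appear only in an optional list: "Other issues for discussion may include pending patients, patient updates, summary of safety reports, and case report form completion".

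**The concern.** A criterion for findings from other studies is meant for information that arises outside the trial. Declaring it inapplicable would make sense only if there could be no such information. The protocol itself names a second HCW9218 protocol, and the qualifier also covers animal and in vitro work, which does not depend on any other trial.

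The drug is new to humans. Section 2.2.3 says "HCW9128 has not yet been evaluated in human clinical studies" (the drug code is transposed there), and Section 7.1 warns that combining the two mechanisms may bring additional or more severe adverse events. With so little in-trial information, a serious finding on the same molecule from elsewhere would matter to FDA's oversight of this IND and to the team deciding whether to open the next cohort. At stake are the timeliness of an IND safety report and the completeness of what the team has before it at each decision.

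**Working it through.** No sample size, power or error rate is in dispute, so there is no plan figure to reproduce. The check sets the sections side by side.

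1. **Does the plan know of outside sources?** Yes. The Synopsis and Section 3 name a competing HCW9218 protocol. Section 2.2.2 summarises nonclinical work on the drug.

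2. **Whose duty is the FDA row?** This study's. Section 11.3 describes a locally sponsored IND, and Section 10.3 has the study submit to FDA as an amendment to the IND, with a copy to the supplier.

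3. **With item 3 disabled, what FDA route is left?** The 7-day row and items 1 and 2 of the 15-day row do not say whose patients they cover. But the table names other studies separately and then excludes them, so the natural reading is that those rows concern this trial's participants. What is left is the row for all other events under CFR 312.32, reported with the annual report. A serious outside finding would then move from 15 days to the annual cycle, or, being a finding rather than an event here, to no row at all.

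4. **Is an outside finding a required input to cohort decisions?** No.
   - Stage 1 moves on in-trial pre-defined events and DLTs (Sections 6.2.1 and 6.2.2).
   - In Stage 2 each cohort is "sequentially assigned to the most appropriate dose by the study statistician based on the updated toxicity probabilities" (Section 13.1), and those probabilities come from this trial's DLTs.
   - The stopping rule in Section 13.4 uses the same posterior probabilities.
   - The mandatory part of the Section 11.4 review is DLT status, timing and dose level. Safety reports are optional and their source is not stated.

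5. **Do other provisions close the gap?** In part.
   - The IRB row of Section 10.3 includes "New or increased risk" within 5 business days. It is not limited to local patients, but it goes to the IRB, not to FDA or the dose meeting.
   - Section 14.3 has safety updates provided to the IRB.
   - Section 10.1 notes that the supplier provides the Investigator's Brochure, so some supplier information does come in, but no interval is stated.
   - Section 11.3 has quarterly review of the study's progress by the DSMC.
   - The supplier's IIT Manual is cited for sample handling, product receipt, excursions and reordering, not for incoming safety information.

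   None of these is a 15-day FDA report, and none makes review of outside findings a condition of opening a cohort.

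6. **What is still open to benefit?** The revision entry of 29 March 2023 records no DLT from the first through the fourth dose level, so dose level 4 had been reached. What remains is enrolment there up to 9 patients, repeat dosing until progression, and Stage 2 (sample size 24) if a DLT occurs.

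**The case against.** The strongest reply is that this is one table cell. Section 10.3 governs what the study sends out, not what the investigators may consider, and restoring item 3 would by itself put nothing before the dose meeting. A note in a protocol table also cannot waive a duty under 21 CFR 312.32, on which Section 10.1 bases its definitions. The partial routes above are real, and the supply agreement, the IIT Manual, the brochure and the monitoring plan are not among the documents, so a return flow of safety information may be arranged there.

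Much of this stands. It is why the fix has two parts, and why the point is about this protocol's text only. It does not rescue the qualifier: staff will follow the table, and the table points them the wrong way. That a single-centre study generates no outside findings is no answer either, since item 3 concerns findings that arise elsewhere.

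Several stronger readings are tempting but unsupported:

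- A reader might infer that the other trial was already treating patients. The documents call it competing and give no status, enrolment or dose.
- A reader might infer that outside data are barred from dose decisions, or that an MTD would be set against known toxicity. No section forbids using such data; they are simply not required.
- A reader might want to express the harm as the chance of missing a toxicity with one patient per level. That would need an assumed number of outside patients and a single rate across doses, whereas Table 2 has DLT rates rising with dose. It would measure the value of extra patients, not the effect of this wording, and the single-patient steps are largely past.
- A reader might ask for a contractual duty on the supplier. That lies outside the protocol and cannot be judged from it.

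**Conclusion.** The point holds in a limited form. Section 10.3 states a rule that, if followed, would keep a serious outside finding on HCW9218 out of the 15-day FDA report, although the same protocol acknowledges another HCW9218 protocol and runs under its own IND. Separately, review of such findings is not a required input to cohort decisions under Section 11.4.

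The size cannot be put as a number from the documents. In scope it is one reporting criterion and the decisions still to come: dose level 4 up to 9 patients, repeat dosing, and Stage 2 if activated. The conclusion rests on reading the remaining FDA rows as covering this trial's participants, and on the protocol alone, since agreements and manuals that might fill the gap were not available. It does not depend on the other trial being active, because item 3 also covers nonclinical findings and any later study. It is worth correcting because the wording gives a wrong instruction, not merely too little detail, and the correction is small.

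**What to change.** In Section 10.3, delete the five-word qualifier after the dash in item 3 of the 15-day FDA row, so that findings from other studies and from animal or in vitro work fall under the same time limit as items 1 and 2.

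In Section 11.4, move serious HCW9218 findings received from other studies or nonclinical work out of the optional list. Make their review a required item before each remaining cohort opens, recorded in the minutes and in the statistician's confirmatory email that the section already calls for. A nil return is enough when nothing has been received.

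The cost is a wording change in two sections, one added agenda item and occasional extra IND safety reports. No dose, DLT definition, stopping boundary or sample size changes.
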